Study Protocol and Statistical Analysis Plan

Evaluation of Extended Wear Technology

V 2.0

December 20, 2021

NCT04882800

Evaluation of Extended Wear Technology

1 Background

Since its original launch in 2008, the Lyric device has offered hearing impaired patients an invisible and more convenient option when compared to conventional daily wear hearing aids. Designed to be worn in the ear canal for several weeks or months at a time, this extended wear, non-custom hearing aid has gone through several iterations and product improvements in the last decade. These product improvements included an expanded size offering in 2017. However, even with this expanded size offering, discomfort, migration, feedback and sound quality still account for a large number of trial cancellations. These issues are often caused by a less than ideal fit, especially if a patient has narrowing ear canal.

2 Objectives

The primary objective is to determine if patients who have rejected or cancelled Lyric subscriptions within the last two years due to discomfort or feedback, migration or poor sound quality (due to poor fit) rate the investigational Lyric4 devices with a fitting modification as more comfortable than the conventional Lyric4 devices.

There are no secondary objectives.

3 Description of the investigational device

The Lyric4 device is an analog hearing instrument that is deeply inserted in the ear canal. It consists of an electronic module and two seals, a medial and lateral, glued onto the electronic module. Currently, the Lyric4 is available in seven non-custom sizes: XXS, XS, S, M, L, XL, and XXL. The investigational device is made of the same components of the commercially available Lyric4 device, but with a fitting modification which may allow for an improved fit for narrower ear canals and increase the size options.

4 Design of the clinical investigation

This will be an interventional, single group design with two conditions (Lyric4 and Lyric4 with fitting modification) where subjects will wear the currently available Lyric device in one ear and the investigational device in the opposite ear for two weeks; and then switch ears for two additional weeks. Subjects will be blinded as to which device is in each ear.

5 Risks and benefits of the investigational device and clinical Investigation

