Questionnaires; will be completed after each home trial for both devices	Assesses subjective relating to the investigational device/feature	No –These questionnaires were designed for this specific study. They are not validated for clinical outcomes.

All analysis of the results will occur at the conclusion of the study. All study data will be stored digitally. The data will be collected from the participants using paper questionnaires and then be stored in an excel file for analysis. Collection of the questionnaire results will occur on an ongoing basis. The lead investigator will scan the paper questionnaires and send them to the study manager via email. All original copies of the questionnaires will be stored at the investigation site until the conclusion of the study, at which point they will be mailed to the study manager. Only authorized research personnel at the sponsor site will have access to the study results.

9 Statistical design and analysis

A priori sample size estimation was not performed for this investigation, as the investigation is exploratory and does not aim to confirm any effect with statistical significance and power.

This is an exploratory trial and will not have statistical criteria for termination.

The experiment performed within this study is designed to evaluate the efficacy and effectiveness of new fitting characteristics to the Lyric extended-wear hearing technology as compared to the commercially available Lyric device. The statistical hypothesis is that average ratings of wearing comfort with the new technology will be equivalent to or better than the commercially available technology. A qualitative analysis of the questionnaires will be used for data analysis. Qualitative data will be collected as a question, response, and anonymous participant ID for all participants at each device fitting and removal.

Due to the exploratory nature of this investigation, an informal exploration of the data will be performed at the conclusion of the trial. No further statistical analysis is planned.

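### The Section 9 hypothesis accepts an undefined 'equivalent' where the only objective asks for 'more comfortable', and the plan commits to no estimate of the comfort difference

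*Combined protocol and SAP*

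**What the plan says.** **Objective (Section 2).** The question is whether patients who gave up Lyric for fit-related reasons "rate the investigational Lyric4 devices with a fitting modification as more comfortable than the conventional Lyric4 devices". The section adds: "There are no secondary objectives". Section 5 describes the possible benefit in the same direction, and Section 6 ties the questionnaires to the primary objective.

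**Hypothesis (Section 9).** The statistical hypothesis is that "average ratings of wearing comfort with the new technology will be equivalent to or better than the commercially available technology".

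**Analysis (Section 9).** "A qualitative analysis of the questionnaires will be used for data analysis". Then "an informal exploration of the data will be performed at the conclusion of the trial", followed by "No further statistical analysis is planned". On the absence of a sample size, the section explains that "the investigation is exploratory and does not aim to confirm any effect with statistical significance and power".

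**Design (Section 4).** Subjects "wear the currently available Lyric device in one ear and the investigational device in the opposite ear for two weeks; and then switch ears". The second wearing period is as long as the first, and subjects are blinded to which device is in which ear.

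**Measurement (Sections 6, 8 and 9).** Comfort is one of several domains that Section 6 says the questionnaires may cover. Sections 6 and 9 place data collection at each fitting and each removal. The Section 8 table places the questionnaires after each home trial, for both devices. No comfort item or time point is singled out for the comparison.

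**The concern.** Two statements of the study question sit in one short plan, and they are not the same question. The objective needs the new device to be rated better. The hypothesis is also satisfied if the two devices are rated alike, and 'alike' has no margin, scale or rule behind it.

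The planned analysis does not close the gap. With no estimate and no interval, a reader of the report could not tell a finding of no meaningful difference from a finding that too few subjects were studied to say. Either could be described as consistent with the Section 9 hypothesis, although neither answers Section 2. This matters because Section 5 looks ahead from greater comfort to an improved fit rate, and from there to more patients being able to use the device.

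**Working it through.** The documents give no sample size, SD, alpha, power or margin, so there is no figure of the plan's own to reproduce. The check is mainly a comparison of the text.

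**Step 1. What each statement makes of each possible result.**

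| Comfort result | Section 2 objective | Section 9 hypothesis |
|---|---|---|
| Investigational rated better | met | met |
| Rated about the same | not met | can be read as met |
| Too imprecise to tell | not answered | can be read as met, as 'equivalent' has no definition |
| Investigational clearly rated worse | not met | not met |

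The two statements part company in the second and third rows. In the second they disagree by wording. In the third the disagreement is possible because nothing in the plan separates 'equivalent' from 'not shown to differ'.

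**Step 2. Does the planned analysis settle it?** The hypothesis speaks of average ratings, which implies a scored comfort item and a mean for each device. The analysis paragraph commits to neither a mean difference nor an interval. An informal exploration might include them, but the plan does not say so.

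**Step 3. What the design could supply.** Both devices are worn at the same time, so anything common to a period cancels within that period. For one subject, let D be the device effect, E the difference between that subject's two ears, and L any carry-over difference in period 2:

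- period 1 difference (investigational minus conventional) = D + E
- period 2 difference, ears switched = D − E + L
- average = (D + E + D − E + L)/2 = D + L/2

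Averaging removes the ear difference but leaves half of any carry-over difference. That is why the by-period results should be shown beside the average.

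**Step 4. Size of the unreported uncertainty (illustration only).** For a paired mean difference, the 95% CI half-width in SDs of the per-subject difference is t(0.975, n − 1)/√n. The values of n are assumed.

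- n = 10: 2.262/3.162 = 0.715
- n = 20: 2.093/4.472 = 0.468
- n = 30: 2.045/5.477 = 0.373

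At n = 20, for example, an observed difference of exactly zero would have an interval of about −0.47 to +0.47 SD. That is compatible with either device being the more comfortable by nearly half an SD. These widths apply to any paired study of that size. They show what an informal summary would hide, and do not measure the conflict in wording itself.

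**The case against.** The strongest reply is that the study is openly exploratory. It has no test and no success rule, so a margin would have nothing to act on, and asking for an interval is partly a matter of preference. Much of this stands. The exploratory status is good reason to have no sample size calculation, alpha or power, and none is asked for here. It does not reconcile two differently worded questions, and a descriptive estimate with an interval is fully compatible with an exploratory study.

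A second reply is that the governing question is clear enough. Section 2 calls its question the primary objective, Section 6 links the questionnaires to it, and Section 5 uses the same direction. This also stands. A reader might infer that the plan leaves it open which statement governs, but the weight of the document lies with 'more comfortable', and the Section 9 sentence is the one out of line.

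A third reply is that the measurement is less vague than it looks. The reference to average ratings suggests that comfort is scored, and Section 8 points to a rating after each home trial. Both are fair. A reader might infer from the permissive list in Section 6 that no scored comfort item exists. The questionnaire is not in the documents, so that cannot be concluded. What remains is that Sections 6 and 9 also name fittings, that there are two home trials, and that no rating is designated for the comparison.

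**Conclusion.** The point holds as a problem of consistency and interpretability. The Section 9 hypothesis is looser than the only objective, its 'equivalent' is undefined, and the plan promises no estimate of the comfort difference or its uncertainty. It should be fixed, but it does not invalidate the data.

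Two stronger readings are not supported. A reader might infer an inflated type I error or a false claim of equivalence. The plan has no test or decision rule and disclaims any confirmatory aim, so neither follows. A reader might also infer that the sponsor will report a tie as success. The wording permits that reading, but the documents do not say it will happen.

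The text comparison rests on the documents alone. The half-widths of about 0.72, 0.47 and 0.37 SD rest on assumed n of 10, 20 and 30, a scored comfort item, and one averaged difference per subject.

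**What to change.** 1. **Align the wording.** Reword the Section 9 hypothesis to match Section 2 and make no equivalence claim. If non-inferiority is what is intended, state and justify a margin and reword Section 2 accordingly.

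2. **Name the main item and its summary.** In Sections 6 and 9, designate the comfort rating taken after each two-week home trial, in line with Section 8. Report the per-subject investigational-minus-conventional difference averaged over the two periods, with a 95% CI labelled exploratory. Show the same difference for each period, since averaging over the two ear assignments does not remove carry-over.

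3. **Provide for an unscored item.** If comfort proves not to be scored, report for each period how many subjects rate the investigational device better, the same or worse. Give an exact 95% CI for the proportion rating it better among all subjects, counting 'same' as not better.

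**Cost.** A few sentences in Sections 6 and 9 (and Section 2 if non-inferiority is chosen) and a short analysis, with no extra subjects because the switch-ear design already yields the paired data. If the questionnaire collects comfort only as free text, a better/same/worse question may have to be added; the documents do not allow this to be checked. The sponsor should also accept that the interval may show the study to be inconclusive.

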All safety related events will be constantly monitored by the investigators and will immediately reported to the Principle Investigator. Evaluation of any SAE, SADE, or UADE will be conducted promptly using Sonova's standard medical device referral protocol. Confirmed UADEs will be reported to the IRB within 10 days after receiving notice of the event. If it is determined that an event or effect presents an unreasonable risk to subjects, this study, or those parts of the study presenting that risk, will be terminated no later than 5 working days after the determination is made and no later than 15 working days after Sonova USA first received notice of the event.

A safety analysis of the relevant data will be done after the data collection is finished.

Deviations to the statistical plan will be captured and reported in an update to this document, with justification.

If data records are complete from subjects who dropped out of the study early, these data will also be used in the analysis. If the data sets are not complete, they will not be integrated at all. If a subject is dropping out before data collection is finished, the study team will try to complete as many data sets as possible. If a subject drops out before the first study visit the subject will be replaced if possible.

10 Investigation Duration

The investigation is expected to last approximately 8 weeks. The expected duration for participation by the subjects is 4-5 weeks.

11 Data Handling and Management

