Deviations from the study plan to protect the rights, safety and well-being of human participants under emergency circumstances may proceed without prior approval of the sponsor and the EC – such deviations will be documented and reported to the sponsor representative (Study Manager) and the EC as soon as possible. Apart from that the investigator is not allowed to deviate from this study plan unless that deviation does not influence the investigation data.

14 Device accountability

The sub-investigator at site or authorized designee will keep records documenting the following in a written process:

- Names of participants who received, used, returned, or disposed of device
- Date of receipt, identification, and quantity of each investigational device (batch/serial number or unique code)
- Expiry date (if applicable)
- Date(s) of use
- Participant identification

15 Informed consent process

At the beginning of the first appointment, the investigator will hand the consent form to the participant in a private setting and grant sufficient time to read the whole form. The consent form contains detailed information about incentives and reimbursement. Any questions will be answered and the participant will be given sufficient time to decide whether or not they want to participate in the study. After the participant signed two copies of the consent form, the researcher will sign both copies as well and provide one copy to the participant.

In case of changes to the procedures described in the consent form, the participant will be informed at the beginning of an appointment.

Informed Consent will only be obtained by investigation participants who can provide informed consent themselves before enrollment.

16 Adverse events, adverse device effects and device deficiencies

Device deficiencies and all **adverse events (AE)** including all **serious adverse events (SAE)** are collected, fully investigated and documented in the source document and appropriate case report form (CRF) during the entire investigation period, i.e. from participant's informed consent until the last protocol-specific procedure, including a safety follow-up period (ISO_14155, 2020)

Evaluation of any SAE, SADE, or UADE will be conducted promptly using Sonova's standard medical device referral protocol.

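### Section 9's rule for incomplete data sets makes no exception for safety data, so read literally it drops adverse events of early leavers from the final safety summary

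*Combined protocol and SAP*

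**What the plan says.** Three statements bear on the point.

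- **Safety analysis (Section 9).** "A safety analysis of the relevant data will be done after the data collection is finished". The plan does not say which data are relevant, and it names no safety population.
- **Early leavers (Section 9, shortly afterwards).** "If data records are complete from subjects who dropped out of the study early, these data will also be used in the analysis". Then: "If the data sets are not complete, they will not be integrated at all". For participants who are leaving, "the study team will try to complete as many data sets as possible". The plan does not define a complete record or data set.
- **Collection of events (Section 16).** Adverse events, serious adverse events and device deficiencies "are collected, fully investigated and documented in the source document and appropriate case report form (CRF) during the entire investigation period", a period that runs "from participant's informed consent until the last protocol-specific procedure, including a safety follow-up period". There is no exclusion for people who leave early.

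Section 9 also provides for safety oversight while the study runs: "All safety related events will be constantly monitored by the investigators".

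**The concern.** Events are collected from everyone, but the only rule on whose data enter an analysis removes early leavers with incomplete data sets. The rule speaks of the analysis in general and excludes without qualification. It stands in the same section as the safety analysis and close behind it. An analyst who follows the text has no basis for treating safety data differently.

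This matters if leaving early is related to having an event. Section 7 recruits people who rejected or cancelled Lyric because of discomfort, feedback, migration or fit-related poor sound quality, so withdrawal after an ear problem is plausible. The exclusion of people who cannot tolerate the physical fit may reduce this but does not remove it. Events that are not serious depend most on the final summary, because they could fall outside expedited reporting. A participant whose device comes out early because of canal pain, and who then withdraws, could have a properly documented event that never appears in that summary.

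**Working it through.** **Figures in the plan.** There is none to reproduce. Section 9 says "A priori sample size estimation was not performed for this investigation", and no section gives an expected dropout rate or event rate. The check is first textual, then an illustration on assumed values.

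**Step 1: does any text restrict the rule?** Section 9 does not tie it to ratings, comfort or questionnaires. Section 16 says how events are collected and reported, not who enters the analysis. Section 11 has a case report form kept for each enrolled participant, and Section 16 puts adverse events on that form. Events can therefore be read as part of a participant's data. No section exempts them.

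**Step 2: can an early leaver have an incomplete data set?** Under Section 4 each participant wears one device in each ear for two weeks, then switches ears for two more. Under Section 6 questionnaires follow each fitting and removal. Someone who leaves before the switch has no ratings from the second period. On an ordinary reading that set is incomplete, although the missing definition leaves room for argument.

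**Step 3: what would the omission do to the event proportion?** Let

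- d = share of participants with incomplete records
- r_c = proportion with an event among those with complete records
- r_i = proportion with an event among those with incomplete records

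Then

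- proportion shown if incomplete records are dropped = r_c
- true proportion = (1 − d) × r_c + d × r_i
- understatement = true − shown = d × (r_i − r_c)

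All values below are assumptions, with r_c = 5%, so the summary shows 5% in every row.

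| d | r_i | True proportion | Understatement |
|---|---|---|---|
| 10% | 5% | 0.9 × 5% + 0.1 × 5% = 5.0% | 0 points |
| 10% | 50% | 0.9 × 5% + 0.1 × 50% = 9.5% | 4.5 points |
| 10% | 100% | 0.9 × 5% + 0.1 × 100% = 14.5% | 9.5 points |
| 20% | 5% | 0.8 × 5% + 0.2 × 5% = 5.0% | 0 points |
| 20% | 50% | 0.8 × 5% + 0.2 × 50% = 14.0% | 9.0 points |
| 20% | 100% | 0.8 × 5% + 0.2 × 100% = 24.0% | 19.0 points |

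The bias vanishes only when r_i equals r_c. If leavers had fewer events than others, the sign would reverse and the summary would overstate the proportion.

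**The case against.** The strongest reply is that the rule was written for questionnaires. Section 8 describes the data for analysis as paper questionnaires transferred to a spreadsheet, and Section 9 says the analysis will be a qualitative one of those questionnaires. A questionnaire set is something a team can try to complete; a spontaneous adverse event is not. Adverse events are also the natural content of a safety analysis of relevant data. This reading is reasonable and may well be what was meant. It stands as a reason to treat the point as an ambiguity, but it does not close the gap, because the plan never says so.

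Three further points stand in full:

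- The rule turns on completeness of records, not completion of the study. Early leavers with complete records are kept, so a reader who infers that only completers are analysed goes too far.
- A reader might infer that participants are less well protected. The documents do not support that. Monitoring, evaluation of serious and unanticipated events, reporting and termination for unreasonable risk (Sections 9 and 16) do not depend on complete data sets.
- A reader might infer that a diluted summary would be used to confirm the Section 5 statement that ear health risk does not exceed that of an ordinary Lyric trial. That statement is a risk justification made in advance. No section makes it a hypothesis for the safety analysis, and no comparator rate is given.

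The exploratory purpose explains the absence of power and formal tests. It does not explain an undefined safety population.

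**Conclusion.** The point holds as a conflict between a collection rule that covers everyone and an unrestricted exclusion rule. It is not proof that events will be lost, since the questionnaire-only reading remains open. Its reach is the end-of-study safety summary alone.

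The direction of any bias rests on one assumption the documents make plausible but do not establish: that early leavers with incomplete records have more events than others. The size cannot be determined from the documents. The table gives 0 to 19 percentage points, and that range depends entirely on the assumed 5% rate in complete records and the assumed 10% or 20% with incomplete records. Any single figure for the understatement would be one chosen scenario. The plan should still be changed, because the sentence that causes the problem is explicit and the remedy needs no new data.

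**What to change.** Add to Section 9, in substance:

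- The completeness rule for early leavers applies to questionnaire ratings only.
- The safety analysis includes all adverse events and device deficiencies collected under Section 16 from informed consent onward, whatever the participant's completion status.
- Events after fitting are listed by the device in the affected ear at onset and by period (before or after the switch). Events before any fitting are listed separately.

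The starting point should be consent, not attempted insertion, to match Section 16. Section 8 lists cerumen management and ear mold impressions among the study procedures, and an event there in someone never fitted would otherwise be missed. Device at onset and period are needed because after the switch each ear has worn both devices.

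The cost is a few sentences and one listing or table from data already collected. The downside is that the reported event rate may look less favourable. If the rule was always meant for questionnaires only, the change simply records that.

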The product-related risks and the clinical investigation procedure-related risks are well-controlled during the clinical investigation as the subject is under the care of a well-established, Lyric-trained, hearing health care provider. Any ear health risk from this investigation is no greater than any risk a hearing impaired patient experiences when undergoing a Lyric trial with a certified Lyric provider.

The study may reveal that the investigational devices are more comfortable for those patients who were unable to wear Lyric devices previously, thus implying an improved fit rate. The investigational devices are not custom, and do not require extensive modifications of the Lyric component itself. If improved fit rate can be confirmed, it is

likely that more hearing impaired patients who would like to experience the benefits of an extended wear device would be able to do so.

6 Endpoints

To satisfy the primary objective, subjective questionnaires will be administered after each device fitting and removal. Question domains may include, but are not limited to, comfort, occlusion, feedback, sound quality, and purchasing interest.

7 Inclusion and Exclusion Criteria

Inclusion criteria: Hearing loss N2-N4 (mild to moderate)

Hearing impairment: Any (conductive or sensorineural)

Population: Adults

Minimum Age: 18 years

Maximum Age: 90 years

Other: Previous Lyric users who rejected or cancelled Lyric trials or subscriptions due to discomfort, feedback, migration, or poor sound quality due to fit issues.

Exclusion criteria: Participants who can only wear a size XXS Lyric will be excluded as even an XXS investigational device would likely not be any more beneficial than a conventional XXS Lyric4 device.

Asymmetrical hearing loss

Other diagnosis that may cause fluctuations in hearing (i.e. Meniere's disease)

Unable to tolerate the physical fit of a Lyric device

Inability to be seen for 4 lab visits

8 Measurements and procedures

Investigation related procedures:

Study Procedure	Impact on subject	Standard of care?
Audiogram; may be done if most recent audiogram is more than 12 months old	Assesses hearing loss	Yes
Cerumen management	Clears ear canal of wax	Yes
Ear mold impression; may be done for future analysis of ear shape	Takes custom impression of ear	Yes

Fit with Lyric devices	Provides prescriptive amplification	Yes

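### Section 9 leaves out incomplete data sets, so participants who stop early because a device is uncomfortable can vanish from the comfort comparison, the trial's only objective

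*Combined protocol and SAP*

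**What the plan says.** Section 9 has two rules for early drop-outs. The first keeps some of them: "If data records are complete from subjects who dropped out of the study early, these data will also be used in the analysis". The second covers the rest: "If the data sets are not complete, they will not be integrated at all". Neither complete nor data set is defined, so the unit could be a participant, a wear period or a single questionnaire. When someone is leaving, "the study team will try to complete as many data sets as possible". Replacement is foreseen only for drop-out before the first visit.

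Four other parts of the plan bear on this:

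- **Objective (Section 2).** Comfort of the modified device against the conventional one. There are no secondary objectives.
- **Design (Section 4).** "subjects will wear the currently available Lyric device in one ear and the investigational device in the opposite ear for two weeks", after which the ears are switched for another two weeks.
- **Population (Section 7).** "Previous Lyric users who rejected or cancelled Lyric trials or subscriptions due to discomfort, feedback, migration, or poor sound quality due to fit issues".
- **Hypothesis (Section 9).** "average ratings of wearing comfort with the new technology will be equivalent to or better than the commercially available technology". The analysis is qualitative and informal, with nothing further planned.

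The timing of the questionnaires is stated in two ways. Section 6 says "subjective questionnaires will be administered after each device fitting and removal", and Section 9 agrees. Section 8 says "Questionnaires; will be completed after each home trial for both devices". Section 9 does not say which time point supplies the average comfort rating.

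**The concern.** Whether a participant counts in the comfort average can depend on comfort. Early stopping for discomfort is foreseeable in people who have already given up the product over fit. Because both devices are worn together, a participant who stops after some days of wear holds the within-person comparison that the trial was set up to obtain.

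The direction of the bias depends on who stops:

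- **Either ear can trigger stopping, at the same level of discomfort.** Leaving stoppers out pulls the device difference towards zero. If the modified device is the less comfortable one, the result moves towards the stated hypothesis. If it is the more comfortable one, its benefit is understated.
- **One device triggers most of the stopping.** That device looks better among completers than it was among everyone fitted, and the two groups can differ in sign.

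Having no formal test does not help, because a descriptive mean over completers carries the same selection.

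**Working it through.** The plan states no figure to reproduce: it gives no sample size, rating scale, SD, correlation or early-stop rate. Every input below is therefore an assumption. Differences are modified minus conventional device, in rating points.

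**1. What the rule removes under each reading**

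| Meaning of data set | Early removal is rated and counts as complete | Early removal is not rated, or counts as incomplete |
|---|---|---|
| Wear period | Nothing lost | Stopped period lost |
| Participant | Whole participant lost if stopping in period 1 leaves the set incomplete | Whole participant lost |

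Sections 6 and 9 suggest that an early removal is rated. Section 8 leaves it open.

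**2. Stopping triggered by either ear**

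Inputs: bivariate normal comfort in the two ears, SD 2, correlation between ears 0.3, 0.5 or 0.7, 70% of variance stable across the two periods, true difference -1.0. A participant stops when either ear falls below one common cutoff, set so that 10%, 20% or 30% stop in either period. Two million participants were simulated per setting. Each cell gives correlation 0.3 / 0.5 / 0.7.

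| Stop early | Completers only | Stopped period deleted |
|---|---|---|
| 10% | -0.88 / -0.91 / -0.94 | -0.90 / -0.93 / -0.95 |
| 20% | -0.80 / -0.85 / -0.89 | -0.84 / -0.87 / -0.91 |
| 30% | -0.74 / -0.80 / -0.85 | -0.78 / -0.83 / -0.88 |

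Using the rating from every period begun gives -1.01 to -1.03. The loss among completers runs from 1 - 0.94 = 6% to 1 - 0.74 = 26%. The sign never changes in this model, and a true difference of +1.0 gives the mirror image. Repeat runs agree within 0.01.

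**3. Stopping triggered by one device**

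Inputs: a single wear period, conventional mean 6, SD 2, correlation 0.5, stopping when the named device is rated below 4.

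| True difference | Device that triggers stopping | Share removed | Difference in completers |
|---|---|---|---|
| 0 | Modified | 15.9% | +0.29 |
| 0 | Conventional | 15.9% | -0.29 |
| -0.5 | Modified | 22.6% | -0.11 |

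With no true difference and stopping on either device, 25.5% are removed. The difference stays near 0, but both means rise from 6.0 to about 6.7.

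**4. When the sign can change**

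Let f be the share who stop, dC the mean difference in completers and dS that in stoppers. The difference in all fitted participants is (1 - f) x dC + f x dS.

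With dC = +0.3 and dS = -3:

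- f = 10%: 0.9 x 0.3 - 0.1 x 3 = -0.03
- f = 20%: 0.8 x 0.3 - 0.2 x 3 = -0.36
- f = 30%: 0.7 x 0.3 - 0.3 x 3 = -0.69

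The sign reverses once f exceeds 0.3 / 3.3 = 9.1%. With dS = +3 the same shares give +0.57, +0.84 and +1.11, so completers then understate the benefit. If f = 0 or dS = dC, nothing changes.

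**The case against.** The strongest reply is that the rule may cost little or nothing.

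- **Reading.** The plan speaks of one departing participant having several data sets, which suggests a unit smaller than the participant. If the unit is the wear period and every early removal is rated, as Sections 6 and 9 can be read, no rating is lost. That reading is open and would remove the problem. But the plan does not choose it, Section 8 points elsewhere, and complete is undefined.
- **Stop rate.** Section 7 excludes people who cannot tolerate the physical fit of a Lyric device, and some participants gave up Lyric for reasons other than comfort. Both points may bring stopping below the assumed 10% to 30%. Neither rules it out.
- **Sign reversal.** The values dC = +0.3 and dS = -3 were chosen to show what is possible. In the either-ear model, stoppers differ in the same direction as completers, by roughly -1.3 to -2.1. A reversal needs a difference near zero and stopping mainly on one device, and nothing in the plan points to that.
- **Direction.** Shrinkage towards zero is conservative for the objective in Section 2, which asks whether the modified device is more comfortable. It is not conservative for the hypothesis in Section 9, which is also met when the devices are equal.
- **Stakes.** The study is exploratory, its questionnaires are not validated, and it has no decision rule. Discomfort that counts as an adverse event is still recorded under Section 16. This lowers the stakes, but an adverse event record does not put a rating back into the comfort average.

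These points limit the size of the problem. They do not remove it.

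**Conclusion.** The concern holds. Read as written, the rule can select on the outcome, and nothing else in the plan returns an incomplete set to the comparison. Under either-ear stopping, 6% to 26% of a 1-point difference is lost at 10% to 30% stopping if whole participants are removed, and 5% to 22% (1 - 0.95 to 1 - 0.78) if only the stopped period is removed. One-sided stopping can move the difference by about 0.3 to 0.4 points, in either direction. A change of sign is possible but needs stronger assumptions. All of this depends on an assumed SD, correlation and stop rate, and on early removals being either unrated or treated as incomplete. The change is worth making even in an exploratory study; confidence in the size is moderate.

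**What to change.** Replace the incomplete-data rule in Section 9 with the following:

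- The comfort measure is the rating of each device at removal, whenever removal occurs, compared within person.
- A participant who stops early contributes every wear period begun.
- At an early removal both ears are rated that day, so that the two ratings cover the same wear time.
- Days worn and the reason for early removal are recorded.
- Early removals for discomfort are reported by device.
- Participants who completed both periods are shown on a second line, and ratings at fitting separately.

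Align Section 8 with Section 6, so that a questionnaire is completed at each removal, including an early one.

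The cost is a few sentences, two data fields and one extra completion of an existing form at an early removal. Section 14 already records dates of use, so days worn may need no new collection. No scheduled visits or participants are added.

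There are two trade-offs. Early ratings cover fewer than 14 days, and the difference from someone with only one period still contains any left/right ear difference that the switch would have cancelled. Showing completers separately lets the reader judge both.
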